# 7 Investigational Medicinal Product

Lu AF82422 is a human IgG1 monoclonal antibody that recognizes all major species of  $\alpha$ -synuclein.

## 7.1 Treatment Regimen

#### 7.1.1 Treatment Regimen Double-blind Period

Patients will be randomly allocated via a centralized randomization system (IRT) to one of two treatment groups:

- Lu AF82422 CCI
- placebo

Patients will be randomly allocated in ratio 2:1 Lu AF82422 and placebo.

Patients will receive IMP starting from the Baseline Visit to follow a Q4W dosing schedule with either Lu AF82422 or placebo by IV infusion. Any deviation from the Q4W ±3 days dosing schedule must be discussed and agreed with the medical monitor and documented as a protocol deviation. IMP dosing must not take place if less than 2 weeks until the next scheduled IMP infusion.

All patients will receive double-blind treatment with IMP starting at baseline (Week 0) until Visit 18 (Week 48), however, some patients will continue to receive treatment up to Visit 24 (Week 72). The individual treatment period will vary from 48 weeks up to 72 weeks based on the timing of the last patient randomized. Once the last patient reaches Week 48, this visit will be the EoTDBP Visit for that patient. Patients who have not completed the visit at Week 72 at the time of Last Patient EoTDBP Visit will have their next visit converted to an EoTDBP Visit with assessments as listed for Visit 24, according to Panel 2. During the DBP, patients will attend IMP Visits to follow a dosing schedule with either Lu AF82422 or placebo Q4W. Patients who do not consent to the optional OLE will enter the Safety Follow-up Period after the EoTDBP Visit.

# 7.1.2 Treatment Regimen Open-label Extension Period

Patients will receive Lu AF82422 CCI.

In the OLE, all patients will receive open-label treatment with Lu AF82422 starting at Visit 1E until Visit 24E (Week 92E) (see Panel 3).

During the OLE period, any deviation from the Q4W ±3 days dosing schedule must be discussed and agreed with the medical monitor and documented as a protocol deviation. IMP dosing must not take place if less than 2 weeks until the next scheduled IMP infusion.

After Visit 25E, or if prematurely discontinued, patients will be scheduled for a Safety Follow-up Visit 20 weeks after the last IMP dose, as scheduled in Panel 3.

## 7.2 IMP(s), Formulation(s), and Strength(s)

The IMP(s) supplied by Lundbeck in this study are:

- Lu AF82422 solution for infusion 53 mg/mL expected dose
- Placebo to Lu AF82422 solution for infusion

At each visit the patient will receive of Lu AF82422 or placebo.

From each of vials assigned in the IRT, ccl solution will be drawn and transferred to an empty infusion bag (to contain the total of ccl of IMP) and the bag will be covered. Doses will be administered by IV infusion over 30 minutes including flush of the infusion line with saline (±10 minutes).

IMP can be prepared at bed side or at the pharmacy thereafter it is transferred to the clinic for administration. In order to maintain the blind, the IMP will be prepared by unblinded, qualified study personal. Preparation has to be undertaken as soon as practicable before administration. Based on in-use stability study, shelf life on product in infusion bag is maximally 4 hours. The date and time of expiry should be stated on the dosing unit label. Details of preparation of IMP for administration are described in the *IMP Manual/Infusion guide*.

In the US, preparation can be done outside a laminar flow cabinet bench based on microbial challenge tests performed. Details of IMP administration will be described in the *IMP Manual/Infusion guide*.

In case of mild or moderate systemic hypersensitivity reaction, which is not an anaphylactic reaction, the IMP should be administered going forward in this patient with slower infusion rate (over 1 hour instead of 30 minutes). This procedure does not avoid a hypersensitivity reaction but helps reduce the severity of any potential reoccurrence. The patient must be withdrawn from treatment if in the opinion of the investigator the reaction contraindicates further dosing.

#### After IMP Administration

Patients will be monitored for immediate drug reactions for a minimum of 2 hours after IMP administration with vital signs taken every 30 minutes (±5 minutes) from the end of the saline flush or until stable, whichever is later (only applicable through Visit 12E). Beginning at Visit 13E, blood pressure and pulse will only be measured immediately prior to and immediately after IMP administration, inclusive of the saline flush (±5 minutes). Vital signs will be documented in the electronic case report form (eCRF).

As with any antibody, allergic reactions to IMP administration are possible. The clinical criteria for defining anaphylaxis for this study are listed in Appendix III. Appropriate drugs, such as epinephrine, antihistamines, corticosteroids, etc., and medical equipment to treat acute anaphylactic reactions must be immediately available at the study sites, and study personnel should be trained to recognize and respond to anaphylaxis according to local guidelines.

If an anaphylactic reaction or a systemic hypersensitivity reaction occurs, a blood sample will be drawn from the patient as soon as possible after the event. For details see section 11.1.3.

## 7.3 Manufacturing, Packaging, Labelling, and Storage of IMP

The IMP(s) will be manufactured, packaged, labelled, released (by a qualified person [QP]), and distributed in accordance with the principles of *Good Manufacturing Practice* (GMP), under the responsibility of Lundbeck.

The IMPs will be provided in single dose vials of 20 mL each as solution for infusion.

The wording on the labels will be in accordance with GMP regarding labelling and national and/or local regulatory requirements. If additional information is to be added when the IMP is dispensed to the patients, this will be clearly stated on the labels, and the investigator will be instructed to do so.

No manipulation, repackaging, or relabeling of IMP is permitted after QP release by Lundbeck, unless a repackaging/relabeling agreement exists, and the documentation is available to Clinical Supply, Lundbeck, and, where necessary, new QP releases are made.

[figure not shown]
The IMP(s) will be identified using a unique medication number.

The IMPs must be stored in a safe and secure location, and in accordance with the storage conditions specified on the labels.

## 7.4 Method of Assigning Patients to Treatment

IRT will be used in this study. Each patient will be assigned a screening number by the IRT, and that number will be used to identify the patient throughout the study. When a patient is to be randomized, the investigator or a designated, unblinded site staff will use the IRT. The IRT allocates the patient to a treatment group and assigns the patient a randomization number in accordance with the specifications from Biostatistics, Lundbeck.

Randomization will take place at Visit 2 after confirmation that the participant continues to meet the inclusion/exclusion criteria. Patients will be randomized 2:1 to receive either study drug or placebo.

In the optional OLE period, all patients will receive Lu AF82422.

## 7.5 IMP Accountability

IMP accountability is documented in the IRT and using IMP forms.

The investigator and the designated, unblinded site staff must agree to only dispense IMP to patients randomized in the study. The designated, unblinded site staff must maintain an adequate record of the receipt and distribution of the IMP(s). This record must be available for inspection at any time.

## 7.6 Unblinding Procedures

Global Patient Safety, H. Lundbeck A/S, and the designated, unblinded site staff will have access to the unblinded information for the double-blind treatment for each patient. Access to these details will be via IRT.

Lu AF82422 is eliminated through proteolytic degradation and not metabolized through CYP P450 enzymes, thus no drug-drug interactions are expected and treatment with Lu AF82422 would not prevent any acute medical or surgical intervention.

The investigator may only break the code for a patient if knowledge of the IMP is necessary to provide optimal treatment to the patient in an emergency situation. If possible, if the investigator needs medical guidance, the investigator should consult the clinical research associate (CRA) and/or in some cases the medical monitor before breaking the code. The investigator must record the date and reason for breaking the code. If the emergency situation was an adverse event, it must be recorded on an *Adverse Event Form*. The CRA and the medical monitor must be notified immediately. The IRT will capture the date and time of the code break call. Information on the allocated treatment will be provided during the call and by email. When the code is broken for a patient, the patient must be immediately withdrawn from the study. If this occurs during a visit, the investigator must complete the visit as a Withdrawal Visit; otherwise, the patient will be asked to attend a Withdrawal Visit.

## 7.7 Post-study Access to IMP(s)

Post-study access to the IMP will not be available. Patients in the study will have access to appropriate medical care after they complete or withdraw from the study.

## 8 Concomitant Medication

#### 8.1 Concomitant Medication

Concomitant medication is any medication other than the IMP that is taken during the study, from 3 months prior to Screening Visit up until the Safety Follow-up Visit.

The concomitant medications that are disallowed or allowed with restrictions during the study are summarized in Appendix II.

Details of all concomitant medications (prescription and over-the-counter) taken <3 month(s) prior to the Screening Visit must be recorded in the eCRF at the first visit. Any changes (including reason for changes) in concomitant medication must be recorded at each subsequent visit. If medically necessary, initiation of or change of dose of concomitant medication is allowed per investigator discretion.

Any new concomitant treatment should not be initiated the same day as a visit with IMP infusion, unless for immediate treatment of a drug reaction or in case of an emergency.

For any concomitant medication for which the dose was increased due to worsening of a concurrent disorder after enrolment in the study, the worsening of the disorder must be recorded as an adverse event (see section 11.1.1).

For any concomitant medication initiated due to a new disorder after enrolment in the study, the disorder must be recorded as an adverse event.

#### 8.2 COVID-19 Vaccination

There is currently no data indicating that Lu AF82422 may interact with or impair the body's immunological response to the COVID-19 vaccines. Hence, there are no indications for safety concerns of concomitant use of the COVID-19 vaccines with Lu AF82422. As such, COVID-19 vaccination is allowed during this study with the guidance measures as described below.

The patient should not receive a COVID-19 vaccination (or any concomitant medication, see section 8.1) the same day as an IMP infusion. If the patient has recently received a COVID-19 vaccine, the investigator should judge if the patient can be administered the IMP infusion at the scheduled visit based upon the patient's individual response to the COVID-19 vaccine.

In the current study, if a patient is administered a COVID-19 vaccine, this should be captured as concomitant medication in the eCRF, including the date that the vaccine was given. The name of the manufacturer and, if applicable, whether it was the "first, second or booster, etc." vaccination should also be added, in a bracket.

All adverse events, including those judged by the investigator to be related to the COVID-19 vaccine must be captured in the eCRF on the *Adverse Event Form*. A causality assessment, including an alternative causality as relevant, must be provided on the *Adverse Event Form*.

## 9 Study Visit Plan

#### 9.1 Overview

The study concept components are presented in Panel 1 and the patient flow is also presented in Panel 1. An overview of the procedures and assessments to be conducted during the study and their timing is presented in Panel 2 and Panel 3. Further details are in section 10.

After completing or withdrawing from the study, the patient must be treated in accordance with usual clinical practice.

The study includes the following periods:

- Screening Period (4 weeks)
- Randomization Period (2 weeks)
- DBP (48 weeks to 72 weeks)
- Optional OLE (96 weeks)
- Safety Follow-up Period (20 weeks after last IMP administration)

## 9.2 Screening Period

## 9.2.1 Screening Visit (Visit 1, -6 Week)

Informed consent must be obtained before any study-related procedures are initiated, including washout of disallowed medications. At the US sites, the patients undergoing the additional objective censor-based assessments must provide specific consent as part of the main *Informed Consent Form*. The patient does not have to consent to both objective sensor-based assessments to participate. The Screening Period will occur up to 4 weeks prior to randomization at Visit 2 and have a duration of approximately 4 weeks.

The main procedures performed at screening include signing the informed consent, demographics, diagnosis of MSA-P or MSA-C according to the Gilman criteria, MoCA, relevant history (medical, psychiatric, neurological, family history of MSA), concomitant medication MRI scan for eligibility and, in addition, evidence of MRI abnormalities supporting the diagnosis of MSA, physical and neurological examination, checking inclusion/exclusion criteria, UMSARS score, safety laboratory and other safety assessments. The Screening Visit can be performed over 2 days during the first week of the Screening Period. The MRI scan should be uploaded for central reading no later than 10 calendar days before the Randomization Visit.

All screening procedures are summarized in Panel 2. Assessments are described in detail in section 10.

#### 9.2.1.1 Patient Identification Card

Each patient will be provided with a patient identification card that states, at a minimum, the name of the IMP, the study number, the patient identification number, and the investigator's name and contact information.

The patient identification card should be returned to the investigator upon completion of the patient's participation in the study.

#### 9.2.1.2 Re-screening

Re-screening is only allowed for patients who screen fail for administrative reasons, or who screen fail due to a change in concomitant medication allowed with restrictions within 8 weeks prior to randomization or have previously screen failed due to an eligibility criterion that has since been revised or removed. The patients must otherwise be eligible for the study at the time of screen failure. Re-screened patients will receive a new screening number.

Authorization for re-screening may only be granted by the sponsor's medical expert (or the CRO's medical monitor) after a thorough review of all data from the original Screening Visit.

At the new Screening Visit, the patient and caregiver must sign a new *Informed Consent Form*. At the new Screening Visit, the patient will be assigned a new screening number. A re-screened patient must have an *entirely* new Screening Visit with all screening procedures and assessments performed again, except for the screening MRI scan if performed within the last 3 months. All the eligibility criteria must be re-assessed at the new Screening Visit.

The following information will also be recorded in the eCRF at the new Screening Visit:

- that the patient has previously been screened for the study
- that re-screening has been authorized (by the sponsor's medical expert OR state who)
- the screening number that was assigned to the patient at the original Screening Visit

If a patient is re-screened, no data from the original Screening Visit will be used except for the original screening MRI if not repeated.

A patient may only be re-screened once.

## 9.3 Randomization Period

See section 10.1.1.

#### 9.4 Double-blind Period

### 9.4.1 Baseline Visit (Visit 3, Week 0)

Important procedures at baseline include MRI scan for volumetric and diffusivity measures, application of IMP PK measurement of IMP in blood and CSF, biobanking samples and pregnancy test. The full list of assessments at the Baseline Visit are summarized in Panel 2.

## 9.4.2 General Outline of Visits During Double-blind Period

During the DBP, site visits will be every 4 weeks  $\pm 3$  days with the possibility of completing the assessments over a maximum of 2 consecutive days for a given visit; and if so, then the first day is considered the "Visit" day according to the schedule and at IMP Visits, the visit must be registered in IRT and IMP administered to the patient on the second day. In addition, two telephone visits (Visits 4 and 8) will be conducted during the DBP to record adverse events and concomitant medication.

#### 9.4.3 End-of-Treatment Visit – Double-blind Period

The individual DBP will vary from 48 weeks up to 72 weeks. Once the last patient reaches Week 48, this visit will be the EoTDBP Visit for that patient. Patients who have not completed the visit at Week 72 at the time of Last Patient EoT Visit will have their next scheduled visit converted to an EoTDBP Visit with assessments as listed for Visit 24, as according to Panel 2.

At US sites, a subset of patients and caregivers may be contacted to participate in a Study Experience interview by telephone or web conferencing platform (for example, Microsoft Teams). The Study Experience interview will be conducted within 6 weeks after the completed Exit interview for patients who consent.

Patients who do not consent to the optional OLE will enter the Safety Follow-up Period after the EoTDBP Visit.

## 9.4.4 Safety Follow-up Visit 20 Weeks After Last Dose of IMP – Double-blind Period

A Safety Follow-up is conducted to capture new adverse events that occur during the Safety Follow-up Period as well as to follow-up on the outcome of adverse events on-going at the end of the treatment period. In addition, the following will be collected; blood and urine samples for clinical safety laboratory tests, blood sampling for IMP quantification and anti-drug antibodies (ADAs), vital signs, physical and neurological examination, ECG, C-SSRS assessment, concomitant medication and pregnancy test. The Safety Follow-up Visit must be conducted as a visit to the site. The Safety Follow-up Visit is scheduled 20 weeks after the last dose of IMP.

For adverse events that were on-going at the EoTDBP or Withdrawal Visit and that resolved during the Safety Follow-up Period, the stop date must be recorded. For non-serious adverse

events still on-going at the Safety Follow-up Visit, the *On-going Adverse Event* checkbox on the *Adverse Event Form* must be ticked. SAEs must be followed until resolution, or the outcome is known.

For details of assessments to be conducted at the Safety Follow-up Visit see Panel 2.

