#### 6.4 Withdrawal Criteria

A patient must be withdrawn from the study if:

- The patient withdraws consent (defined as a patient **explicitly** takes back his or her consent); section 9.6 states how the patient's data will be handled
- The patient has been randomized in error and has not been administered IMP
- Withdrawal of patients enrolled in error and who have received the IMP should be based on a case-by-case evaluation of the individual risk/benefit. The decision about the administration of more doses of Lu AF82422 will be based on an individual risk/benefit assessment as judged by the investigator
- The patient can no longer attend study visits due to MSA disease progression.
- The patient is lost to follow-up (defined as a patient who fails to comply with scheduled study visits or contact, who has not actively withdrawn from the study, and for whom no alternative contact information is available [this implies that at least two documented attempts have been made to contact the patient])

A patient must be withdrawn from treatment if:

- The patient experiences any systemic hypersensitivity reaction to IMP infusion which are confirmed as anaphylactic reaction by a clinically relevant increase of serum total tryptase from baseline level (see section 11.1.3)
- The patient experiences any severe and/or serious systemic hypersensitivity reactions even though the serum total tryptase does not confirm an anaphylactic reaction
- The patient experiences an adverse event that, in the opinion of the investigator or sponsor's medical expert, contraindicates further dosing
- The investigator considers it, for safety, lack of efficacy, and/or study compliance reasons, in the best interests of the patient that he or she be withdrawn from treatment
- Any site personnel breaks the randomization code for that patient
- The patient becomes pregnant
- The patient has a serum ALT or AST value >3 times the upper limit of the reference range and a serum total bilirubin value >2 times the upper limit of the reference range
- The patient has a serum ALT or AST value >5 times the upper limit of the reference range that is confirmed by testing <2 weeks later
- The patient has a QTcF interval >500 ms confirmed on repeat, if the repeat is done within 72 hours; the decision to withdraw the patient may be postponed until a repeat ECG is taken, if it is taken within 72 hours during the DBP.
- A patient may be withdrawn from the study if:

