# 9.5.2 Safety Follow-up Visit Open-label Extension Period 20 Weeks After Last Dose of IMP

A Safety Follow-up Visit of the extension period (SFU-E) is conducted to capture new adverse events that occur during the Safety Follow-up Period as well as to follow-up on the outcome of adverse events on-going at the end of the treatment period. In addition, the following will be collected; blood and urine samples for clinical safety laboratory tests, blood sampling for IMP quantification and ADA, vital signs, physical and neurological examination, C-SSRS assessment, concomitant medication and pregnancy test. The Safety Follow-up must be conducted as a visit to the site. The Safety Follow-up Visit is scheduled 20 weeks after the last dose of IMP.

For adverse events that were on-going at the EoTOLE, or Withdrawal Visit and that resolved during the Safety Follow-up Period, the stop date must be recorded. For non-serious adverse events still on-going at the Safety Follow-up Visit, the *On-going Adverse Event* checkbox on

the Adverse Event Form must be ticked. SAEs must be followed until resolution, or the outcome is known.

The Safety Follow-up Visit for patients who withdraw consent must be performed, if at all possible; any information collected will only be recorded in the patients' medical records.

For details of assessments to be conducted at the Safety Follow-up Visit, see Panel 3.

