#### 9.6 Withdrawal Visit

Patients who withdraw from the study prior to the respective EoT Visit for the treatment period (ie, EoTDBP or EoTOLE) will be asked to attend a Withdrawal Visit and Safety Follow-up Visit, if at all possible. If the patient cannot attend the site physically for the Withdrawal Visit, and the visit would then not be performed, the visit should be performed as a remote or Telemedicine visit with assessments performed as described in the "COVID-19 Mitigation Plan", if possible. The Withdrawal Visit must be scheduled as soon as possible after withdrawal.

No new information will be collected from patients who withdraw from the study, except information collected in relation to the scheduled Withdrawal Visit and the Safety Follow-up Visit 20 weeks after last dose of IMP or needed for the follow-up of adverse events (section 11.5).

MRI scanning is only to be performed as an EoT/withdrawal procedure if it was not performed within the last 8 weeks.

Patients who withdraw during a period with fall diary entries must return the diary at the Withdrawal Visit.

Patients who withdraw during a period with objective sensor-based assessments must return the sensor(s) at the Withdrawal Visit.

The Exit interview will be conducted within 3 weeks after the Withdrawal Visit for patients who have been in the DBP for at least 48 weeks prior to withdrawal. For patients who withdraw from study treatment after Week 48 in the DBP and complete an Exit interview, patients may be contacted to participate in a Study Experience interview.

The reason for withdrawal must be recorded in the eCRF.

For a patient who withdraws consent:

• if the patient withdraws consent during a visit and then agrees to it being the final visit, the investigator will complete the visit as the Withdrawal Visit and all the data collected up to and including that visit will be used.

- if the patient withdraws consent during a telephone conversation, the investigator will ask the patient if he or she will attend a Withdrawal Visits. If the patient:
  - -agrees to attend a Withdrawal Visit, all the data collected up to and including these visits will be used
  - -refuses to attend a Withdrawal Visit, the investigator should attempt to follow the patient's safety and future treatment; any information collected will only be recorded in the patient's medical records

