16.9 Events of Death

Events of deaths will be summarized by treatment group, reason of death and study period . In addition, events of death will be listed.

Time-to-death will be investigated graphically using a Kaplan Meier plot and modelled, if applicable, by applying a Cox proportional-hazards model incl. treatment group, CCl and region as covariates. For patients with no unique date-of-death the date of the last completed visit will be used. Patients still alive at the time of the safety follow-up visit will be censored using the date of the last safety follow-up visit as last observed time point.

17 Pharmacokinetic/Pharmacodynamic Analysis

The population pharmacokinetics of Lu AF82422 will be determined by means of non-linear mixed effect analysis. Estimated parameters of plasma exposure per patient (e.g. AUC and Cav) will be related to the efficacy and safety/tolerability in an exploratory PK/PD analysis. Details of the popPK and PK/PD analyses will be given in a separate popPK/PD analysis plan. The results of the popPK and PK/PD analyses will be reported in a popPK/PD report and relevant parts of it might be given in the clinical study report.

18 Immunogenicity Analysis (ADA)

The analysis of anti-Lu AF82422 antibodies will be performed for all subjects in the APTS receiving at least one dose of Lu AF82422. Subjects receiving placebo will not be analyzed for anti-Lu AF82422 antibodies.

Pre-existing ADA	Refers to antibodies reactive with the biologic drug that are present in subjects be- fore drug administration
Treatment-induced ADA	ADA developed de novo following drug administration
Treatment-boosted ADA	Pre-existing ADA that were boosted to a higher-level following drug administra- tion, i.e., titer is greater than the baseline titer by a fourfold increase
Neutralizing ADA (NAb)	ADA that inhibits or reduces the pharmacological activity of the drug
ADA-positive subject	A subject with at least one treatment-induced or treatment-boosted ADA-positive sample at any time during the treatment or follow-up observation period
ADA-negative subject	A subject without a treatment-induced or treatment-boosted ADA-positive sample during the treatment or follow-up observation period
ADA-inconclusive subject	A subject who cannot irrefutably be classified as ADA-negative since drug is present in the same sample at a level exceeding the validated drug tolerance level, i.e., drug tolerance

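### The Safety Follow-up Visit is site-only, with no remote fallback for patients withdrawn because progression stops them attending, so new events and vital status at 20 weeks may not be actively ascertained

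*Protocol*

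**What the plan says.** The site requirement appears twice in the protocol. Section 9.4.4 (double-blind period): "The Safety Follow-up Visit must be conducted as a visit to the site". Section 9.5.2 (OLE): "The Safety Follow-up must be conducted as a visit to the site". Neither section mentions another mode.

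Section 6.4 lists, among the grounds on which a patient must leave the study: "The patient can no longer attend study visits due to MSA disease progression". Section 4.1 keeps everyone except consent withdrawals on schedule for the follow-up 20 weeks after the last dose. Section 9.6 says that patients who withdraw "will be asked to attend a Withdrawal Visit and Safety Follow-up Visit, if at all possible".

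Section 9.6 also holds the only remote option. It begins "If the patient cannot attend the site physically for the Withdrawal Visit, and the visit would then not be performed" and continues that "the visit should be performed as a remote or Telemedicine visit", with assessments taken from the COVID-19 Mitigation Plan. It names the Withdrawal Visit and nothing else. The section then stops further data collection after withdrawal, with three exceptions: the Withdrawal Visit, the Safety Follow-up Visit, and whatever adverse event follow-up under section 11.5 requires.

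For time-to-death, SAP 16.9 states: "Patients still alive at the time of the safety follow-up visit will be censored using the date of the last safety follow-up visit".

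**The concern.** Read together, these rules send a patient who has been withdrawn because travel is no longer possible to a visit that requires travel. The protocol foresaw the same difficulty for the Withdrawal Visit and solved it there, but did not carry the solution forward to the follow-up.

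The missing data would not be a random subset. Those who cannot attend are the patients who have progressed most, and one would expect events and deaths to concentrate among them. Three things are exposed: active detection of new adverse events in the post-dose window that the sponsor chose to observe, concomitant medication over that window, and confirmed vital status at its end. The time-to-death summary also lacks a defined end point for living patients who never reach the visit.

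**Working it through.** **1. The calendar.** The plan's own durations reproduce.
- Double-blind period: the last dose is at Week 44 or Week 68. 44 + 20 = 64 and 68 + 20 = 88. Adding the 6 weeks before baseline gives 70 and 94 weeks, as in section 4.1.
- OLE: the last dose is at Week 92E. 92 + 20 = 112, matching Panel 3. 6 + 48 + 112 = 166 and 6 + 72 + 112 = 190, as in section 4.1.
- The end-of-treatment visit falls 4 weeks after the last dose, so the follow-up comes 20 − 4 = 16 weeks later. If a Withdrawal Visit has the same spacing (an assumption), the stretch without a completed visit is 16 weeks. At the half-life of about 30 days in section 2.1.3, that is 112 / 30 ≈ 3.7 half-lives. The full 20 weeks is 140 / 30 ≈ 4.7.

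**2. The path of one patient.** Progression prevents attendance, so section 6.4 applies. The Withdrawal Visit may be remote (section 9.6). The follow-up is still scheduled (section 4.1) but must be on site (sections 9.4.4 and 9.5.2). The qualifier in section 9.6 excuses absence without offering another route. Section 15 rules out permission to deviate, so a site that telephoned instead would be recording a deviation.

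**3. What reaches the database by another route.**

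| Item at the follow-up | Route if the visit is missed | Recovered by a remote contact? |
|---|---|---|
| SAEs already known | Followed to outcome (sections 9.4.4, 9.5.2, 11.5) | Already covered |
| New SAEs and deaths | Reportable within 24 hours of awareness (section 11.4), but no contact is specified to prompt awareness | Yes |
| New non-serious adverse events | Recorded at the follow-up visit (section 11.5) | Yes |
| Concomitant medication | None stated | Yes |
| Vital status, if alive | None stated | Yes |
| C-SSRS | None stated | Where feasible |
| Laboratory, PK, ADA, vital signs, examinations, ECG (double-blind only) | None | No |

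**4. The SAP.** Section 16.9 ties censoring to the follow-up visit date. The preceding rule in that section, on the last completed visit, addresses patients with no unique date of death. It does not say that it applies to living patients who missed the follow-up. Section 16.1.4 uses the same visit to close the adverse event periods.

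**5. Scale.** Inputs: 60 patients and 20% overall drop-out (section 17.12). 60 × 0.20 = 12. The share leaving for this reason is not given, so assume 25% to 75%: 12 × 0.25 = 3 and 12 × 0.75 = 9, which is 5% to 15% of 60. These are upper counts, because some may still attend. The 20% belongs to the sample size for the double-blind period; no OLE drop-out rate is stated.

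**The case against.** The strongest reply is that these patients are not lost. They remain scheduled for the follow-up and are asked to come. Section 9.6 expressly exempts that visit and adverse event follow-up from the stop on data collection. Death is an SAE (section 11.1.1), worsening of MSA that meets a seriousness criterion is reportable, and SAEs volunteered even after the follow-up are handled (section 11.5). US patients with at least 48 weeks in the double-blind period also have an Exit interview within 3 weeks of withdrawal that may bring up adverse events. All of this stands. A reader might infer that the sickest patients have no safety or survival data, or no planned contact, after withdrawal. The documents do not support either reading. What remains is that discovery of new events becomes passive, and that the interview comes well before 20 weeks and only for some patients.

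Second, most of the visit needs physical attendance, which explains the site rule. That is a good reason to keep it as the default, but not to forgo what a call can collect.

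Third, the withdrawal criterion entered with Edition 6.0, whose transitional rule concerns patients waiting between Visits 12E and 13E. By inference the double-blind period was then over or nearly so. A reader might infer a loss that differs between randomised arms. That is weakly supported, because everyone in the OLE receives active drug.

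Fourth, the COVID-19 Mitigation Plan is not available and might permit a remote follow-up. Section 9.6 invokes it for the Withdrawal Visit, whereas sections 9.4.4 and 9.5.2 do not mention it.

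Finally, time-to-death is graphical, modelled only if applicable, and outside the testing sequence, so no confirmatory conclusion is at risk.

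**Conclusion.** The point holds as a gap in ascertainment. Patients withdrawn because progression stops them attending have no specified remote route to the 20-week follow-up, so active enquiry about new adverse events, concomitant medication and vital status may be lost, and the loss is related to progression. SAP 16.9 leaves living patients without that visit with no stated censoring date.

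The size is uncertain and probably small. The figure of 3 to 9 patients rests on the assumed 25% to 75% share and on none of them attending, and it borrows the double-blind drop-out rate for an effect that probably falls mainly on the OLE. The conclusion also assumes that the unseen COVID-19 Mitigation Plan does not already cover this visit. The primary and key secondary analyses are unaffected. The change is worth making because it is cheap and because the unreached patients are those most likely to have events.

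**What to change.** In protocol sections 9.4.4 and 9.5.2, keep the site visit as the default and add a fallback. If the patient cannot attend, a remote contact by telephone or telemedicine, with the caregiver where needed, records at least vital status and its date, new and ongoing adverse events, concomitant medication and, where feasible, the C-SSRS. If the COVID-19 Mitigation Plan already provides this, refer to it in both sections.

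In SAP 16.9, censor living patients at the last date known alive, including the date of that contact.

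The cost is a sentence in each of two protocol sections, a sentence in the SAP, and a call per affected patient. The contact modes already exist: Visits 4 and 8 are telephone visits for adverse events and concomitant medication (section 9.4.2), and section 9.6 accepts telemedicine. The limitation is that laboratory, PK, ADA, ECG, vital sign and examination data remain missing for these patients, as they would under the current text.
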